## 1.0 Objectives

The primary aim of the study is to validate a proprietary cuffless blood pressure algorithm using measurements from a chest-worn medical device, the Perin Health Patch (PHP). The study will compare the performance of the PHP to an ambulatory blood pressure cuff across 85 subjects for a 20-minute monitoring period and confirm that the wearable device performance meets AAMI standards. The specific objectives are:

- To calculate the mean error and standard deviation of blood pressure (BP) measurements from the PHP relative to the ambulatory blood pressure cuff.
- To determine the compliance of the PHP's mean absolute error (MAE) and standard deviation (SD) with AAMI standards:  $\leq 5$  mmHg MAE with  $\leq 8$  mmHg SD for systolic and diastolic BP.

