## 2.0 Background/Rationale

Hypertension, or HBP, is a major modifiable risk factor for cardiovascular diseases (CVDs), which are the leading cause of death globally [1]. Continuous BP measurements are vital for the early prevention, detection, evaluation, and treatment of hypertension and related CVDs due to its prognostic value for BP variability (BPV) [2]. Non-invasive, continuous monitoring at home can enhance patient management by allowing timely therapy adjustments, early detection of cardiac issues, and better management of chronic cardiac conditions, leading to improved patient outcomes and reduced healthcare costs.

Current hypertension guidelines emphasize the importance of out-of-office BP measurements to confirm elevated BP and monitor changes over time. Continuous monitoring of hemodynamic parameters traditionally requires invasive techniques such as arterial lines. These methods are impractical for home use due to the need for specialized equipment and skilled personnel, along with associated risks like infection and thrombosis [3], [4]. Traditional cuff-based home BP devices, which have been the standard for decades, face limitations such as patient adherence, cuff fit, measurement technique, and physical discomfort. Additionally, these devices cycle every 15-30 minutes and cannot reliably capture BP variability and rapid changes, which are crucial for high-risk patients, especially post-operative ones [5].

Recent advances in photoplethysmographic (PPG) sensors have enabled the development of non-invasive and continuous heart rate (HR) and BP monitoring devices. PPG detects blood volume variations in vessels by measuring changes in light absorption. BP is estimated from pulse transit time (PTT), the time taken by the arterial pulse to travel from the heart to a peripheral site. PTT is related to BP through the pulse wave velocity (PWV), which depends on the elastic modulus of the vessel wall, blood density, and arterial dimensions [6]. However, previous systems have failed to meet clinical thresholds set by the British Hypertension Society (BHS) and AAMI, which require a mean estimation error (MAE) of less than 5 mmHg and a standard deviation of less than 8 mmHg [7]. Challenges include inaccurate BP estimations, the need for regular recalibration, and the influence of complex biological processes like vascular tone on measurements [8], [9], [10].

---

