#### **3.1 Study Design**

This is a prospective study designed to validate the PHP by comparing its BP measurements with those from an FDA-cleared ambulatory BP cuff (Norav NBP One). The study will include 85 participants who will undergo a series of BP measurements over a 20-minute period while simultaneously wearing the PHP and ambulatory BP (ABP) cuff. This study will be conducted in home and office environments, including patients' homes and the offices of Perin Health Devices ([name]). An initial BP measurement will be taken, followed by four reference BP measurements and three paired test device measurements.

The study will also include an optional cold pressor test to further evaluate the device's performance on intra-patient variability. The cold stimulus activates afferent sensory pathways that, in turn, trigger a sympathetic response resulting in an increase in BP. If a subject elects to participate in the cold pressor test, the validation measurements will be repeated after placing their hand in ice water for one minute.

According to AAMI standards, this study design will ensure the mean absolute error (MAE) between the PHP and the reference device does not exceed 5 mmHg with a standard deviation (SD) of  $\leq 8$  mmHg for both SBP and DBP.

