## 4.0 Data/Specimen Analysis

### 4.1 Data Analysis Plan

Blood pressure from the PHP will be calculated using a proprietary algorithmic approach. The steps include:

1. Preprocessing: Areas of high motion, as determined by the accelerometer measurement are excluded from the analysis. For ECG and PPG signals, artifacts such as baseline wandering and respiratory components at lower frequencies, as well as power line harmonics and electromyogram artifacts at higher frequencies are removed. Auscultation signals are filtered to remove lung sound components and concentrate on heart sound components.
2. Segmentation: Fiducials for the ECG, PPG, and auscultation signals are extracted using respective techniques.
3. Depth-Resolved PPG: The time difference between the capillary component (blue LED) and the arteriolar component (red/IR LED) is used to calculate arteriolar PTT and SVR.
4. Feature Extraction: A combination of hand-crafted features and learned feature embeddings are extracted and concatenated into a single feature vector.
5. Deep Learning Estimation: An LSTM-based model is used to estimate SBP and DBP from the calibration value and the input feature vector.

The mean error and standard deviation of the SBP and DBP measurements from the PHP relative to the ambulatory blood pressure cuff will be calculated. Statistical analysis will include paired t-tests and Bland-Altman plots to assess the agreement between the two devices.

The feature extraction and estimation analysis will be conducted by PI [name], blinded to reference values to maintain data analysis integrity, pursuant of the company's conflict of interest policies. The evaluation and statistical comparisons against the ABP cuff will be conducted by Co-I [name] with independent validation by [name], an independent reviewer. The criteria for validation will follow AAMI standards, where the mean difference must be  $\leq 5$  mmHg and the standard deviation  $\leq 8$  mmHg.

---

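### The 5 mmHg acceptance limit applies to mean absolute error in 1.0 and 3.1 but to mean difference in 4.1, so the same data can pass one rule and fail the other

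*Combined protocol and SAP*

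**What the plan says.** Four sections of the combined protocol and SAP state or use the 5 mmHg criterion.

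- **1.0 Objectives.** The first objective is descriptive and uses the signed error: "To calculate the mean error and standard deviation of blood pressure (BP) measurements from the PHP". The second carries the acceptance limits (5 mmHg, with SD at most 8 mmHg, for systolic and diastolic pressure) and uses the absolute error: "To determine the compliance of the PHP's mean absolute error (MAE) and standard deviation (SD) with AAMI standards".
- **2.0 Background/Rationale.** The thresholds are described as ones "which require a mean estimation error (MAE) of less than 5 mmHg". The abbreviation MAE is attached to a phrase that does not contain the word absolute.
- **3.1 Study Design.** The limit is again on the absolute error, written out in full: "this study design will ensure the mean absolute error (MAE) between the PHP and the reference device does not exceed 5 mmHg".
- **4.1 Data Analysis Plan.** The limit moves to the signed error: "The criteria for validation will follow AAMI standards, where the mean difference must be" at most 5 mmHg, with SD at most 8 mmHg. The quantities to be calculated are "The mean error and standard deviation of the SBP and DBP measurements from the PHP relative to the ambulatory blood pressure cuff", and then: "Statistical analysis will include paired t-tests and Bland-Altman plots to assess the agreement between the two devices". MAE does not appear.

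Sections 1.0, 3.1 and 4.1 all attribute their rule to the AAMI standards. None says which statistic governs.

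**The concern.** The primary aim is a pass/fail validation, and the documents give two pass/fail rules. A mean difference measures systematic offset: a device that reads far too high in half the participants and far too low in the other half can have a mean difference of zero. An MAE measures typical error size and gives no credit for cancellation. The plan as written could therefore declare the device valid under 4.1 while the second objective in 1.0 is not met, or is never evaluated, because 4.1 does not provide for calculating MAE.

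Section 3.8 says the data will be used in a regulatory approval. If the governing statistic is still open when results are available, the rule can be chosen to fit them. The blinded estimation and independent validation in 4.1 protect the pressure estimates and the calculations. They do not settle which rule decides.

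**Working it through.** **Inputs from the documents.** 85 participants (1.0, 3.1). Three test readings each in the resting series: "followed by four reference BP measurements and three paired test device measurements" (3.1), so 85 × 3 = 255 pairs if complete. Limits of 5 and 8 mmHg (1.0, 3.1, 4.1). The documents give no expected bias, error SD, error distribution or within-participant correlation, and do not say whether the unit is the pair or the participant mean. They contain no pass-rate figure to reproduce.

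**Step 1: relation between the rules.** For any errors e, |mean(e)| ≤ mean|e|. If the SD in both rules is that of the signed errors, and 4.1 is read as |mean difference| ≤ 5, every dataset passing the MAE rule passes the mean-difference rule. The converse does not hold.

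**Step 2: a conflict with no distribution assumed.** Take 42 participants at +7, 42 at -7 and one at 0.

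- Mean = 0
- SD = √(84 × 49 / 84) = 7.00
- MAE = 84 × 7 / 85 = 6.92

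This passes 4.1 (0 ≤ 5, 7.00 ≤ 8) and fails 1.0 and 3.1 (6.92 > 5). Give each participant the same error three times and pool the 255 pairs: mean 0, SD = √(252 × 49 / 254) = 6.97, MAE 6.92. The verdicts conflict again, so the contradiction does not depend on the unit of analysis.

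**Step 3: where the rules part under normal errors.** For errors with mean m and SD s,

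MAE = s√(2/π)·exp(−m²/2s²) + m(1 − 2Φ(−m/s)).

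At m = 0 this is 0.798s. An SD of 8, the largest that 4.1 allows, gives MAE 6.38. MAE ≤ 5 needs s ≤ 6.27 at m = 0, and s ≤ 5.93, 5.46 or 4.64 at m = 2, 3 or 4.

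**Step 4: pass rates.** Simulation of 20,000 trials per setting, 85 participants × 3 pairs, normal errors, zero bias, intraclass correlation (ICC) 0.5. Both rules also require signed SD ≤ 8. All of these settings are assumptions.

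| Single-pair SD | Pooled pairs: mean difference | Pooled pairs: MAE | Participant means: mean difference | Participant means: MAE |
|---|---|---|---|---|
| 5.5 | 100% | 99.2% | 100% | 100% |
| 6.0 | 100% | 78.7% | 100% | 99.9% |
| 6.5 | 100% | 27.2% | 100% | 98.3% |
| 7.0 | 99.6% | 3.1% | 100% | 87.8% |
| 7.5 | 90.2% | 0.1% | 100% | 62.2% |

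Participant means are milder because averaging shrinks the SD: 7.0 × √((1 + 2 × 0.5)/3) = 5.72.

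Sensitivity at single-pair SD 7.0:

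- Over ICC 0.2 to 0.8, the MAE rule passes 1.5% to 6.4% pooled, and 100% down to 32% with participant means.
- With Laplace errors at ICC 0.5, the mean-difference and MAE rules pass 94% and 56% pooled, and 99.8% and 98% with participant means.
- If the 85 participant means themselves have SD 7.0, the figures are 97% and 10%.

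No simulated 85 × 3 trial passed the MAE rule and failed the mean-difference rule, as Step 1 requires.

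**Step 5: why the SD must be defined too.** If the SD beside MAE were that of the absolute errors, the nesting in Step 1 fails. With 20 errors of +20, 20 of -20, 108 of +2 and 107 of -2, the mean is 0.01, MAE 4.82, SD of absolute errors 6.56 and SD of signed errors 8.15. That would pass 1.0 and fail 4.1. The signed SD is the natural reading, but no section states it.

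**The case against.** The best defence is that MAE is a labelling slip and mean difference was always meant. Section 4.1 is the analysis plan and the only place that sets out criteria for validation. Everything it calculates rests on signed differences. The first objective is also mean error, section 4.2 justifies 85 participants by detecting a mean difference, and section 2.0 shows the abbreviation used loosely. An analyst would probably apply 4.1.

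That is a fair reading, and it may be the intended one. But 1.0 and 3.1 spell out the absolute error in full, so if it is a slip, both are wrong as written on the acceptance criterion. If it is not, 4.1 is wrong. An edit is needed either way. Which statistic the cited standard requires cannot be settled from these documents, and nothing here depends on it.

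A second objection is that the most striking pass rates come from a selected region. This stands as a limit on size: the rules agree almost always at single-pair SD 5.5 or below under the Step 4 model, and analysis by participant means narrows the gap considerably. It does not touch the example in Step 2, which needs no model.

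**Conclusion.** The concern holds and must be fixed. The acceptance statistic for the primary aim differs between the objectives and design (1.0, 3.1) and the analysis plan (4.1), and the two can return opposite verdicts on the same data. That conclusion rests only on the text and on the arithmetic of Step 2.

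The likelihood of conflict is not established, because error SD, bias, shape, correlation and unit of analysis are all unstated. It runs from negligible at low SD to near certain with pooled pairs at single-pair SD 7.0. With the SD taken on signed errors, the conflict goes only one way: 4.1 is the more lenient rule. Confidence in the contradiction is high.

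**What to change.** Before the data are seen, the sponsor should name one governing statistic, give the reason, and state it identically in 1.0, 3.1 and 4.1, correcting the label in 2.0.

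- **If mean difference governs:** require |mean of signed errors, PHP minus reference| ≤ 5 mmHg and SD of signed errors ≤ 8 mmHg, each for SBP and for DBP. The absolute-value sign matters, because 4.1 read literally would pass a large negative bias. Report MAE descriptively, and say openly that this is less strict than the rule now in 1.0 and 3.1.
- **If MAE governs:** add the calculation of MAE to 4.1, apply the 5 mmHg limit to it, and define the accompanying SD as that of signed errors. Section 4.2 would also need revisiting, since its sample-size statement concerns a mean difference.

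Section 3.3 dates the study June to September 2024. If results have already been seen, report both statistics against the limits and disclose that the governing one was chosen afterwards.

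The cost is wording, with no new data. The first choice gives up the stricter bar now stated in 1.0 and 3.1. The second means a device that passes 4.1 may fail: under the Step 4 assumptions at single-pair SD 7.0, the pass rate falls from 99.6% to 3% with pooled pairs, or from 100% to 88% with participant means, and barely changes at SD 5.5.

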## 2.0 Background/Rationale

Hypertension, or HBP, is a major modifiable risk factor for cardiovascular diseases (CVDs), which are the leading cause of death globally [1]. Continuous BP measurements are vital for the early prevention, detection, evaluation, and treatment of hypertension and related CVDs due to its prognostic value for BP variability (BPV) [2]. Non-invasive, continuous monitoring at home can enhance patient management by allowing timely therapy adjustments, early detection of cardiac issues, and better management of chronic cardiac conditions, leading to improved patient outcomes and reduced healthcare costs.

Current hypertension guidelines emphasize the importance of out-of-office BP measurements to confirm elevated BP and monitor changes over time. Continuous monitoring of hemodynamic parameters traditionally requires invasive techniques such as arterial lines. These methods are impractical for home use due to the need for specialized equipment and skilled personnel, along with associated risks like infection and thrombosis [3], [4]. Traditional cuff-based home BP devices, which have been the standard for decades, face limitations such as patient adherence, cuff fit, measurement technique, and physical discomfort. Additionally, these devices cycle every 15-30 minutes and cannot reliably capture BP variability and rapid changes, which are crucial for high-risk patients, especially post-operative ones [5].

Recent advances in photoplethysmographic (PPG) sensors have enabled the development of non-invasive and continuous heart rate (HR) and BP monitoring devices. PPG detects blood volume variations in vessels by measuring changes in light absorption. BP is estimated from pulse transit time (PTT), the time taken by the arterial pulse to travel from the heart to a peripheral site. PTT is related to BP through the pulse wave velocity (PWV), which depends on the elastic modulus of the vessel wall, blood density, and arterial dimensions [6]. However, previous systems have failed to meet clinical thresholds set by the British Hypertension Society (BHS) and AAMI, which require a mean estimation error (MAE) of less than 5 mmHg and a standard deviation of less than 8 mmHg [7]. Challenges include inaccurate BP estimations, the need for regular recalibration, and the influence of complex biological processes like vascular tone on measurements [8], [9], [10].

---

Our study aims to validate a proprietary cuffless BP measurement algorithm using a chest-worn medical device, the Perin Health Patch (PHP). This algorithm leverages the multimodal sensing capabilities of the wearable health patch, which combines noise-immune auscultation, electrocardiography (ECG), pulse oximetry via photoplethysmography (PPG), bioimpedance (BioZ), skin temperature, and motion and tilt sensors. The PHP integrates multiwavelength PPG (MWPPG) with blue, green, red, and IR LEDs, allowing for precise calculation of PTT, PWV, and related unique parameters such as pre-ejection period (PEP) and systemic vascular resistance (SVR). This comprehensive approach aims to improve the accuracy and long-term stability of BP estimations by incorporating biological system knowledge and modeling nonlinear relationships between measured and estimated BP values, consequently improving systolic BP (SBP) and diastolic BP (DBP) estimations.

### **3.0 Study Design and Procedures**

This study will be conducted in strict accordance with the ethical principles outlined in the Declaration of Helsinki (2013). Ethics approval will be sought and obtained from the relevant institutional review board before the initiation of the study. All participants will be provided with detailed informed consent forms, ensuring that they fully understand the nature of the study, their rights as participants, and the potential risks and benefits involved. The consent forms will emphasize the voluntary nature of participation, ensuring that participants are free to withdraw from the study at any time without penalty. Additionally, measures will be implemented to protect the privacy and confidentiality of all participants, including the secure handling and storage of data. Throughout the duration of the study, the well-being, autonomy, and dignity of all participants will be upheld and respected.

#### **3.1 Study Design**

This is a prospective study designed to validate the PHP by comparing its BP measurements with those from an FDA-cleared ambulatory BP cuff (Norav NBP One). The study will include 85 participants who will undergo a series of BP measurements over a 20-minute period while simultaneously wearing the PHP and ambulatory BP (ABP) cuff. This study will be conducted in home and office environments, including patients' homes and the offices of Perin Health Devices ([name]). An initial BP measurement will be taken, followed by four reference BP measurements and three paired test device measurements.

The study will also include an optional cold pressor test to further evaluate the device's performance on intra-patient variability. The cold stimulus activates afferent sensory pathways that, in turn, trigger a sympathetic response resulting in an increase in BP. If a subject elects to participate in the cold pressor test, the validation measurements will be repeated after placing their hand in ice water for one minute.

According to AAMI standards, this study design will ensure the mean absolute error (MAE) between the PHP and the reference device does not exceed 5 mmHg with a standard deviation (SD) of  $\leq 8$  mmHg for both SBP and DBP.

### 3.2 Study Type

This study is a Prospective Review: the data do not currently exist and will be collected over the course of this study to conduct the validation.

### 3.3 Date Range of Data

The study will be conducted from June 15, 2024 to September 15, 2024.

### 3.4 Study Procedures

The study will be conducted in environments where the PHP is expected to be used, including in participants' homes, office environments, and clinical environments. The study will be conducted in a private environment away from other people. There will be no costs to subjects for participating in the study. Subjects will not be compensated for their participation.

The study will be conducted by the following steps:

1. Participants will be identified through self-selection via an online form shared broadly across social media, email, and web. The online form will include: (1) a description of the study (2) overview of the risks and benefits (3) contact information form. See Appendix E for the online form overview. For participants who elect to participate, they will be contacted by the study team to schedule a time to conduct the study. If the participant is not able to be contacted by phone, a follow-up email will be sent.
2. During the scheduled time, the participant will be provided with an overview of the study, including the study's purpose, procedures, risks, and benefits, and will be given the opportunity to ask questions. The participant will then be asked to sign and complete the consent form. The consent form will be scanned and stored securely in an electronic format for the study team. The physical copy will be returned to the participant.
3. The participant will complete an intake form to gather demographic and medical history information. Information collected will be any exclusion criteria, age, sex, height, weight, ethnicity, history of disease, history of smoking, and history of hyper- or hypotension. On this intake form, the subject will indicate whether they are willing and able to undergo the cold pressor test.
4. For patients with significant chest hair that would occlude the optical measurement, the participant will be asked to shave the region where the device will be placed. The study team member will then measure the skin tone. This skin tone image will be taken against a calibration color palette to normalize all images and an objective skin tone will then be calculated using a detailed representation using a multidimensional measure of apparent skin color [11]. Study team members should be sure that the face is not captured in the skin color photo.
5. The application site will be cleaned using an alcohol wipe and the PHP will be adhered to the participant's chest. The ABP cuff will be placed on the left arm, following the procedure outlined in their instructions for use (IFU).

---

6. The validation procedure starts with the subject seated comfortably and relaxed for at least 5 minutes, her/his back and arm supported with the middle of the upper arm at heart level, legs uncrossed, and feet flat on the floor. Talking and any other interference will be avoided throughout the entire validation procedure.
7. A timer is started and an initial measurement is taken: a reference BP measurement ( $R_0$ ) followed by a test device measurement ( $T_0$ ) to confirm the PHP function. A calibration measurement using a third BP device will be taken when  $T_0$  is taken to calibrate the PHP.
8. Four reference BP measurements follow, alternated by three test device measurements ( $R_1-T_1-R_2-T_2-R_3-T_3-R_4$ ) (See Table 1).  $R_x$  measurements will be performed with 2-minute intervals, with  $T_x$  measurements occurring 15 seconds after an  $R_x$  measurement. The recordings will be synchronized using absolute time measurements as well as a timer that is started.
9. The participant will optionally undergo the cold pressor test if they indicated on the intake form that they are willing and able to participate. If they opt not to undergo the cold pressor test, skip to Step 10. If they do opt to undergo the cold pressor test, the hand contralateral to the arm with the ambulatory blood pressure cuff will be submerged in ice water ( $\leq 5^{\circ}\text{C}$ ) for at least 1 minute. The study team member will record the temperature of the ice water at the start of the cold pressor test. The participant may opt to remove their hand at any time if they are experiencing high levels of discomfort. After 1 minute the participant will be instructed to remove their hand.
10. Validation measurements from Table 1 will be repeated as soon as the subject removes their hand. Four reference BP measurements follow, alternated by three test device measurements ( $R_1-T_1-R_2-T_2-R_3-T_3-R_4$ ) (See Table 1).  $R_x$  measurements will be performed with 2-minute intervals, with  $T_x$  measurements occurring 15 seconds after an  $R_x$  measurement.
11. Following the completion of the measurements, the ABP cuff will be removed from the participant. The participant may also be provided with a hand warmer as the following steps are completed.
12. The participant will complete a 5-question survey of Likert-type questions related to comfort and usability of the PHP (See Appendix C).
13. The PHP will then be removed from the participant's chest. The study team members should be sure to use the adhesive remover to minimize any pain or discomfort from the removal of the adhesive.
14. The participant will be discharged from the study and provided with follow-up contact information along with a copy of the consent form.

If the investigator or participant notes an adverse reaction during the testing period, any monitoring devices will be removed immediately, and the subject will be discharged from the study.

**Table 1.** Procedure for reference and test device BP measurements in sequential validation method.

Initial BP measurements for device function confirmation and calibration		
1.	Take reference BP measurement from BP device.	R 0
2.	Take test device BP measurement, calibration measurement	T 0 , C 0
Validation BP measurements for accuracy evaluation		
3.	Take first reference BP measurement	R 1
4.	Take first test device BP measurement	T 1
5.	Take second reference BP measurement	R 2
6.	Take second test device BP measurement	T 2
7.	Take third reference BP measurement	R 3
8.	Take third test device BP measurement	T 3
9.	Take fourth reference BP measurement	R 4

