### 6.0 Consent Process & HIPAA Authorization

#### 6.1 Consent Process

Participants will be identified through self-selection via an online form shared broadly across social media, email, and web. The online form will include: (1) a description of the study (2) overview of the risks and benefits (3) contact information form. See Appendix E for the online form overview. For participants who elect to participate, they will be contacted by the study team to schedule a time to conduct the study. If the participant is not able to be contacted by phone, a follow-up email will be sent.

The consent process will take place in a private setting before any study procedures are performed. Participants will be informed, in English, about the study's purpose, procedures, risks, and benefits, and will be given the opportunity to ask questions.

Participants will be made aware that there will be no negative impacts if they refuse to participate. Consent will be obtained by either PI [name] or Co-I [name] from participants engaging in the study. The participant will be provided with a physical copy of the informed consent documentation and asked to provide a signature. The consent form will be scanned and stored securely in an electronic format for the study team. The

physical copy will be returned to the participant. The study procedure may occur immediately after receiving consent.

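### No visible step uses the resting blood pressures or the collected history to withhold the optional cold pressor test

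*Combined protocol and SAP*

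**What the plan says.** Under section 3.4, step 3, the intake form collects, among other items, "history of disease, history of smoking, and history of hyper- or hypotension". On the same form "the subject will indicate whether they are willing and able to undergo the cold pressor test". The cuff is placed at step 5. R0 is taken at step 7, where the plan adds "A calibration measurement using a third BP device will be taken when" T0 is taken; this is C0 in Table 1. R1 to R4 follow at step 8.

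Step 9 then states: "The participant will optionally undergo the cold pressor test if they indicated on the intake form that they are willing and able to participate". It goes on to distinguish those who opt in from those who do not, which may be a second decision, but it is again the participant's own.

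Section 3.1 describes the expected effect as a sympathetic response that raises blood pressure. Section 8.1 mentions discomfort in connection with the test. Section 5.2 excludes pacemaker patients but sets no blood pressure limit.

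On the analysis side, section 4.1 has the PI carry out feature extraction and estimation "blinded to reference values to maintain data analysis integrity". It also says "An LSTM-based model is used to estimate SBP and DBP from the calibration value and the input feature vector".

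**The concern.** The participant declares fitness for the test before any study blood pressure has been taken. The readings that bear most directly on whether a pressor stimulus is sensible arrive afterwards, and the rule in step 9 does not refer to them. It does not refer to the history either, although that is on the same form as the mark.

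Followed as written, the visible procedure sends an opted-in participant with severely raised resting readings into an optional stimulus expected to raise them further, possibly at home. No step says that participants are told their readings, so their continuing choice need not reflect them. The stake is participant safety in an add-on test, not the validity of the resting comparison.

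**Working it through.** The plan gives no figure to reproduce, and the point rests on no alpha, power or effect size. The check is to put the steps in order and look for any place where a blood pressure value or the history can stop the test.

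1. **Order of events (section 3.4).** Consent discussion at step 2; history and opt-in mark at step 3; cuff placed at step 5; R0, T0 and C0 at step 7; R1 to R4 at step 8; immersion at step 9. The mark precedes every study reading.

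2. **Readings available before immersion.** R0 to R4 give 5 and C0 gives 1, so 5 + 1 = 6 resting readings. Table 1 assigns R0 and C0 to function confirmation and calibration, and R1 to R4 to accuracy evaluation. It assigns none to a decision about the test.

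3. **Places where a hold could sit.**
   - Step 9: depends on the participant's mark and choice only.
   - Inclusion and exclusion (5.1, 5.2): no blood pressure limit. The pacemaker exclusion applies to the whole study.
   - Intake history (step 3): collected, but no visible rule connects it to step 9.
   - Hand removal (step 9): triggered by discomfort, during immersion.
   - Instruction to remove the hand after 1 minute (step 9): limits exposure, not entry.
   - Adverse-reaction discharge (after step 14): reactive, with no blood pressure value defining a reaction.
   - Withdrawal at any time (3.0) and the risk explanation (step 2): both work through the participant.
   - Signal quality index (4.3): concerns signal quality, not safety.
   - IRB approval and non-significant-risk concurrence (Appendix D): oversight of the study, not a check on an individual's readings.

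   None of these uses a resting value or the recorded history to withhold the test.

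4. **Can the readings be used without breaking the blind?** The PI must not see reference values. Section 6.1 says "Consent will be obtained by either PI" or the Co-I, so the PI may be at the session. The plan does not say who runs the cuff program. If it is someone else, that person can apply a limit to R0 to R4. If it is the PI, C0 can serve instead: it comes from a third device and the calibration value already enters the model, so using it discloses no reference value.

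5. **Data cost of a hold.** Each validation block has 3 test-device pairs. A participant held back and sent to step 11 loses the repeat block, which is 3 pairs. The planned pre-immersion block is complete by then: 85 x 3 = 255 pairs, unchanged.

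**The case against.** The strongest reply is that the relevant pages are the ones not shown. The opt-in mark sits on the intake form (Appendix B). The consent form (Appendix A) and the body of the pre-enrollment form (Appendix E) are also unseen, and section 3.5 mentions screening online. Any of these could list contraindications or state when staff withhold the test. This stands. A reader might infer that a form completed by step 3 cannot act on later readings. That goes too far, because a paper form can carry a staff instruction or a section completed later. What can be said is that step 9 refers to no such instruction.

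Second, the documents do not measure the hazard. They give no size for the pressor response, no dangerous resting level and no likelihood of harm from one minute of immersion. This also stands. That a hold is prudent is a clinical judgement built on the plan's own statement that blood pressure rises.

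Third, protection already exists. A team member attends and records the water temperature, the participant is told to remove the hand after 1 minute, pacemaker patients are excluded, an adverse reaction ends participation, and an IRB reviews the study. Section 8.1 words its list as inclusive, so discomfort need not be the only risk considered. These points lower the urgency, but none supplies a check on a blood pressure value.

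Fourth, a hold may leak information. Section 3.8 gives the PI oversight of the electronic and physical data, so an opted-in mark with no immersion hints at high readings or a relevant history. The hint is weak, since the participant may simply have changed their mind, but it should be acknowledged.

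**Conclusion.** The point holds for the visible text: entry to the cold pressor test depends only on the participant's mark and choice, and neither the six resting readings nor the history can withhold it. It is a cheap improvement that should be made, held with medium confidence because part of the paperwork is unseen.

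Its size cannot be put in numbers of participants. The documents give neither the opt-in rate nor the distribution of resting pressures, and no estimate is offered. The conclusion assumes that staff follow the steps as written and that the unseen appendices contain no hold rule. If they do contain one, what remains is to refer to it in step 9.

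Two stronger readings are not supported. A reader might infer that the study has no screening for contraindications; the unseen forms leave that open. A reader might also infer that the accuracy result is compromised; the 255 planned pre-immersion pairs are collected before the test and do not depend on it.

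The instruction "If they opt not to undergo the cold pressor test, skip to Step 10", which sends opt-outs to a step that begins when the hand is removed, is a separate drafting matter and adds nothing to the safety point.

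**What to change.** First ask the sponsor whether Appendix A, B or E already lists contraindications or tells staff when to withhold the test. If not, insert one line between steps 8 and 9:

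*Do not perform the cold pressor test if resting blood pressure is at or above a pre-set limit, or if the intake history shows a listed contraindication; record go or no-go, and send a no-go participant to step 11.*

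- The sponsor and IRB set the SBP and DBP limits, since the documents give no figure. They should state whether the mean or any single reading counts.
- Whoever already runs the cuff program applies the limit to R0 to R4. If that is the PI, apply it to C0 instead. C0 is only one reading, so it is a weaker basis. Confirm that the values used can be seen during the session; section 3.5 does not say.
- Add the expected rise in blood pressure to section 8.1.

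The cost is a short amendment and one recorded line per opted-in participant, with no extra staff. Each no-go loses 3 optional pairs. Some of the high-pressure range is lost from a subset meant to examine intra-patient variability. The PI may gain a small residual hint when an opted-in participant is not immersed. The 255 pre-immersion pairs are untouched.
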